3.3. Analysis Population

The following analysis sets will be identified for this study.

Enrolled Analysis Set: All subjects who sign the ICF for the study are considered to have enrolled.

Intent-to-Treat (ITT) Analysis Set: The ITT Analysis Set will include all randomized subjects. This dataset may also be referenced as the 'Randomized Set'. The ITT subjects may or may not receive randomized treatment. All ITT subjects will be included in the randomized treatment group even if a dosing error occurred. See additional discussion in [Section 3.7](#).

Safety Analysis Set: The safety set will include all ITT Analysis Set subjects who are treated with any study drug (Saline or IC) and will be used for safety and tolerability assessments. In the safety analysis set all subjects will be included in the actual treatment group received if a dosing error occurred. See additional discussion in [Section 3.7](#).

Efficacy Analysis Set: The efficacy analysis set includes all Safety Analysis Set subjects who have a surgical procedure to assess ureteral patency and who have received both study drugs (Saline and IC dose) and a video approximately 10 minutes in length is available after each treatment. **The 21 patients who were randomized and treated prior to the development of the conspicuity score will be excluded from the efficacy population.** This will be the primary population for efficacy assessments. This is also referenced as the modified intent-to-treat (mITT) Analysis Set. All efficacy evaluations will be based on the mITT population. In the mITT analysis set all subjects will be included in the actual treatment group received if a dosing error occurred. See additional discussion in [Section 3.7](#).

Per Protocol (PP) Analysis Set: The PP set includes all subjects from the Efficacy Analysis Set who did not have any major protocol deviation that may confound the interpretation of the efficacy assessment. This Analysis Set will serve as a confirmation analysis set for efficacy analysis. In the PP analysis set all subjects will be included in the actual treatment group received if a dosing error occurred. See additional discussion in [Section 3.7](#).

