3.8.2. IC Treatment Responders

A responder (Yes/No) variable will be derived for each subject by comparing the conspicuity score following IC treatment vs the conspicuity score after saline treatment. When there is ≥ 1 point improvement (IC – Saline) in the conspicuity score and the conspicuity score following the IC treatment is (3, 4, or 5) for a subject, this subject is considered a responder of the IC treatment. The responder assessment will be performed for each ureter separately.

3.8.3. Time to Visualization (TTV) of Blue Color in the Ureteral Jets After IC Administration

Each randomized subject is expected to receive 1 dose of saline and 1 dose of IC; time of each injection, including start time and completion time, will be recorded as HHMMSS (hour, minute, and second). **TTV event is assessed only after IC treatment within 10 minutes after the injection start.** Time when this event occurred after IC injection will be captured as HHMMSS. Therefore, TTV following each injection will be derived as follows.

TTV (minutes) = (time when adequate visualization occurs - start time of injection) / 60

If the adequate visualization of blue color in the ureter jet flow at an ureteral orifice following IC injection for a subject did not occur for any reason, this subject will be censored for this analysis. The censored time will be set to 10 minutes.

TTV will be derived for each subject following IC injection for each ureter separately.

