3.8.3.1. Missing Data Imputation Rules for TTV

In order to calculate TTV, the injection start time and time when blue color is adequate visualized in the ureter jet flow must be present. Although the clinical team will make the best effort to eliminate missing or partial time, mistakes could occur. The following rules will be implemented should a subject had missing or partial injection time or time when blue color in the ureter jet flow is adequately visualized.

1. When the injection start time is missing or partial

- 1) If injection start time is missing but the completion time is present, the missing start time will be set to be the same as the injection completion, and vice versa.
- 2) If the hour and minutes are non-missing but the seconds are missing for injection start time, the first second (01) will be assigned to the injection time.
- 3) Otherwise the median elapsed time (defined as time between surgery start time and injection start time) in the study across all subjects who did not have missing data will be used to impute the missing time. That is, the missing injection start time will be set as (Surgery start time + median elapsed time).

The rules will be implemented based on this order.

2. When event occurred but the time is missing or partial

A subject is considered to have had this event when the conspicuity score is 4 or higher per central reader score for this ureter. When a subject has this event but the time when the event occurred is missing, the following rules will be applied.

- 1) If the time is partial (i.e., only the seconds are missing), the first second (01) will be assigned.
- 2) If the time is missing, the subject will not be censored for this endpoint. The missing time, however, will be assigned to 10 minutes after the injection start time.
- 3) This event will be considered as an important protocol deviation. The subject will be excluded from the efficacy PP analysis set. A sensitivity analysis may be performed for the TTV endpoint based on the efficacy PP analysis set.

If a subject had issue(s) with a ureter initially this subject will be censored for this analysis regardless if the issue(s) is or is not fixed during the procedure.

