5.1. Conspicuity Score from the Central Readers

In this study each subject will serve as his/her own control and each subject will have repeated measures from the same treatment (1 from the left and 1 from the right ureter); therefore, each subject is expecting to contribute 4 observations for conspicuity endpoint. The recording videography will be read by the surgeon (who is unblinded for treatment and blinded for IC dose) and by two center readers who is blinded to the treatment (Saline vs IC) and IC dose. The score from the central readers will be the source for the primary endpoint analysis and the conspicuity score provided by the surgeons will be utilized for concordance analysis (see [Section 5.5](#) for details).

There will be 2 central reviewers to watch each video after the videos are blinded. The ratings are acceptable for consistency if the scores from the two independent reviewers for a ureter under the same treatment are within (+/-) 1 point. In this case, the average score across the two reviewers will be the final score from the central reader. Otherwise, a third independent reviewer (a judicator) will review the same video and this judicator's score will be the final score from the central reader.

As indicated earlier in [Section 3.7](#) the summary table for this endpoint will include 3 treatment groups, namely IC High Dose, IC Low Dose, and Saline Group. It is expected that the sample size (n) for the Saline group will be twice the size of the sample size for the IC High dose and IC Low Dose.

The treatment effect on the conspicuity score will be evaluated using a Generalized Estimating Equation (GEE) for Repeated Measures to control for the intra-subject correlation by fitting a proportional odds model to evaluate the treatment effect. A full model (**Model 1**) will provide the chi-square tests (Score Statistics for Type 3 GEE Analysis) for the effects from treatment (IC High dose / IC Low dose, Saline), ureter (left side ureter vs right side ureter), and treatment*ureter interaction on the response based on multi-normal distribution for an ordinal

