5.1.1. Missing Data Handling Procedure

When conspicuity assessment cannot be performed, conspicuity score will be missing. Reason for each Not Assessed cases will be documented in the database.

- For the primary analysis (Table 14.2.1.1), missing data will not be imputed. Subjects will be included in the input dataset as is. This analysis will be referred to as the Observed Data Analysis.
- However, the impact of missing data will be evaluated by performing 3 sensitivity analyses. The sensitivity analysis will use the same model specified for the primary analysis; nominal p-values from each sensitivity analysis will be reported as. Those 3 sensitivity analyses are described below:
 - Sensitivity Analysis 1 – This analysis will include all MITT subjects who have no missing data. That is, all subjects in this analysis will have 4 conspicuity scores as planned (Table 14.2.1.2).

- Sensitivity Analysis 2 – This analysis will exclude all subjects who are not in the PP population and subjects who have ≥ 1 missing data. This would represent the best outcome for the study since all potential confounded issues will be removed (Table 14.2.1.3).
- Sensitivity Analysis 3 – This analysis will impute the missing data that creates the worst scenario for the study (Table 14.2.1.4).
 - Missing data for Saline Treatment: Assign missing value for saline treatment to be the best value from this patient if scores are available. If no score is available for this patient, then assign the best score of 5 to missing data.
 - Missing score for IC Treatment: Assign missing value for IC treatment to the worst score the patient had if scores are available. If none is available, assign the worst score of ‘1’ to missing data.

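### A missing visualization time removes a subject from the per-protocol set only when the central IC score is 4 or higher, so PP-based analyses are partly selected on the primary endpoint

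*SAP*

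**What the plan says.** Item 2 of SAP 3.8.3.1 deals with a missing or partial visualization time. It first settles whether an event happened: "A subject is considered to have had this event when the conspicuity score is 4 or higher per central reader score for this ureter". It continues: "When a subject has this event but the time when the event occurred is missing, the following rules will be applied". Three sub-rules follow:

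- Sub-rule 1 fills in missing seconds.
- Sub-rule 2 counts a wholly missing time as an event at 10 minutes rather than as a censored observation.
- Sub-rule 3 states: "This event will be considered as an important protocol deviation. The subject will be excluded from the efficacy PP analysis set". It adds that a sensitivity analysis of time to visualization (TTV) on the PP set may be done.

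The score in question is the IC score, because SAP 3.8.3 says: "TTV event is assessed only after IC treatment within 10 minutes after the injection start". Where adequate visualization "did not occur for any reason, this subject will be censored for this analysis. The censored time will be set to 10 minutes"; no deviation or PP exclusion is attached to that case. Item 1 of 3.8.3.1 imputes a wholly missing injection start time, if necessary from a study median, and again states no PP exclusion.

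On the role of the score, SAP 5.1 says: "The score from the central readers will be the source for the primary endpoint analysis". SAP 3.3 builds PP from efficacy-set subjects "who did not have any major protocol deviation that may confound the interpretation of the efficacy assessment".

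PP is used in two main places. Sensitivity Analysis 2 of the primary endpoint (SAP 5.1.1) always uses it, and the SAP comments: "This would represent the best outcome for the study since all potential confounded issues will be removed". The table list in SAP 8.1 also labels that analysis as the best case. SAP 5 repeats the efficacy analyses on PP only if more than 10% of mITT subjects are excluded from it.

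**The concern.** A per-protocol set should be defined by conduct, not by outcome. Here one route out of PP opens only when the central IC score, which is the primary endpoint, reaches 4. A subject whose IC scores are below 4 in both ureters cannot leave PP by this route, whatever was or was not recorded.

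The exclusion also has no clear link to the purpose of PP. An unrecorded clock time does not confound a blinded reading of the video, the responder status derived from it, or the surgeon's satisfaction rating. Yet the whole subject is dropped, including the saline scores and the other ureter. A missing injection start time harms TTV in much the same way, and there the SAP simply imputes.

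At stake is the meaning of Sensitivity Analysis 2. It is presented as the most favourable, least confounded version of the primary analysis, but this rule removes high IC scores from it.

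**Working it through.** **Rule logic.** Consider an IC ureter with no recorded visualization time.

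| Central IC score | Status under SAP 3.8.3 and 3.8.3.1 | TTV | PP |
|---|---|---|---|
| 4 or higher | event, time missing | event at 10 min | subject excluded |
| below 4 (including an averaged 3.5) | no event | censored at 10 min | no exclusion stated |

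The PP consequence differs only by the score.

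**Size.** The plan gives no figure for this, and its sample size assumptions are blacked out, so there is nothing to reproduce. Inputs:

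- N = 116 − 21 = 95 subjects expected in the efficacy set (SAP 3.2 and 3.3).
- p = share of IC ureters scoring 4 or higher: not given; assumed 0.30 to 0.90, with 0.70 as the worked case.
- m = chance that a ureter's time is missing, regardless of score: not given; assumed 2% to 20%.

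*Independent ureters.* A ureter triggers exclusion with probability pm.

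- Share of subjects excluded = 1 − (1 − pm)².
- Retained share at 4 or higher = p(1 − m)/(1 − pm).

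With p = 0.70 and m = 0.10: excluded = 1 − 0.93² = 0.135, or 12.8 of 95. Retained share = 0.63/0.93 = 0.677.

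*Both ureters always on the same side of 4.*

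- Share of subjects excluded = p[1 − (1 − m)²].
- Retained share = p(1 − m)²/[p(1 − m)² + 1 − p].

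Same inputs: excluded = 0.70 × 0.19 = 0.133, or 12.6 of 95. Retained share = 0.567/0.867 = 0.654.

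| m (p = 0.70) | Retained share, independent | Retained share, concordant | Excluded of 95 (independent / concordant) |
|---|---|---|---|
| 2% | 0.696 | 0.691 | 2.6 / 2.6 |
| 5% | 0.689 | 0.678 | 6.5 / 6.5 |
| 10% | 0.677 | 0.654 | 12.8 / 12.6 |
| 20% | 0.651 | 0.599 | 24.7 / 23.9 |

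At m = 10% with independent ureters, other values of p give: 0.30 to 0.278 (5.6 excluded), 0.50 to 0.474 (9.3 excluded), 0.90 to 0.890 (16.3 excluded).

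On the odds scale, the odds of an IC score of 4 or higher are multiplied by 1 − m (independent) or (1 − m)² (concordant). Over m = 2% to 20% that is a factor between 0.98 and 0.64. How far the IC-to-saline odds ratio moves also depends on the saline scores of the excluded subjects, which the documents do not give.

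**Source of the shift.** In a simulation of 2,000,000 subjects with independent ureters, the SAP rule gave 0.677 for p = 0.70 and m = 10%. A rule treating every missing time alike, whatever the score, left the share at 0.700. The shift therefore comes from the score condition and not from losing subjects.

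**The 10% threshold.** 9/95 = 9.5% and 10/95 = 10.5%, so 10 exclusions set off the PP repeats. The worked case passes that on this route alone.

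**The case against.** Several points on the other side stand.

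- **The primary inference is untouched.** It rests on observed mITT data (SAP 5 and 5.1.1), and Type I error control applies to that endpoint only (SAP 3.4). PP is supportive. Sensitivity Analysis 1, on complete cases without PP exclusions, is reported alongside. Passing the 10% threshold only adds an analysis.
- **A blank time below 4 is often correct.** SAP 3.8.3 records a time only when visualization occurs, so a non-event has none by design. A reader might infer that the same lapse is punished for high scorers and forgiven for low scorers; the documents do not establish that in general. It can happen, since level 3 of the scale in SAP 2 allows colour contrast. The arithmetic for the SAP rule does not need it, however: only missing times among ureters at 4 or higher enter the formulas.
- **The size is modest and wholly assumed.** Nothing in the documents supports 10% to 20% missing times, and SAP 3.8.3.1 promises best efforts to avoid them. The worked shift of 2.3 points is about half the standard error of a 70% proportion in 95 subjects, √(0.7 × 0.3/95) = 4.7 points. That is a fair measure of scale, though a systematic shift is not excused by being smaller than sampling error.
- **Not all high scores go.** Only subjects with a high score and a missing time are dropped. In a TTV analysis on PP, events with recorded times remain, and removing events imputed at 10 minutes would make visualization look faster than in mITT.
- **Seconds-only gaps.** A reader might take sub-rule 3 to cover sub-rule 1 as well. That is one reading; the wording follows directly on the wholly missing time and is unclear. Either reading still requires a score of 4 or higher.

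None of this supplies a reason for making PP membership depend on the conspicuity score.

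**Conclusion.** The point holds in a limited form. For a missing visualization time, SAP 3.8.3.1 makes exclusion from PP conditional on a central IC score of 4 or higher, so by this route PP is selected on the primary endpoint. Other deviations can still remove subjects from PP; the criticism concerns this route alone.

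The effect falls on Sensitivity Analysis 2, on any conditional PP repeats and on the optional TTV analysis on PP. For conspicuity it works against IC, contrary to the best-case label. A reader might infer that it threatens the primary result or could create a false claim of benefit. The documents do not support that: the primary analysis does not use PP, and the direction is unfavourable to IC.

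Under the worked assumptions (70% of IC scores at 4 or higher, independent ureters, 10% of times missing per ureter regardless of score), the PP share at 4 or higher falls to about 67.7%, with about 13 of 95 subjects lost. With fully concordant ureters it falls to about 65.4%. If missing times are rare the effect is small, and with none it is zero. It is worth correcting because the edit is simple and the rule serves no purpose for conspicuity.

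**What to change.** In SAP 3.8.3.1, item 2, delete the PP exclusion in sub-rule 3. The lapse can still be recorded as a deviation under SAP 4.4. In SAP 3.3, state that PP membership is decided by deviations identified without reference to conspicuity scores. Keep the affected subjects in PP for the conspicuity, responder and satisfaction analyses.

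Confine missing times to a TTV sensitivity analysis that omits, or varies, the event times imputed at 10 minutes and keeps true non-events censored at 10 minutes. Excluding every ureter without a recorded time would not be sound: it would delete all properly censored non-events and make visualization look faster than it was.

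State whether sub-rule 3 was meant to cover times with only the seconds missing.

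The cost is SAP wording; no new data are needed. The downside is that PP will then include some subjects with a documented time-recording lapse.

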5.4. Time to Visualization

In this study each subject will contribute 2 TTV observations, one for left and one for right ureter. Each time to event observation will be considered an independent observation.

As indicated earlier in [Section 3.7](#) the summary table for this endpoint will include 2 treatment groups, namely IC High Dose, IC Low Dose. Time (minutes) to visualization (TTV) of blue color in the ureter jet flow will be evaluated using the Kaplan-Meier Survival Analysis approach. Descriptive summary, including number of subjects (%) subjects censored; time to event percent-tiles (25%, 50%, and 75%) and 95% confidence intervals and Kaplan-Meier mean (SE) will be estimated for each ureter. The following is an example SAS syntax for this analysis.

```
ods output CensoredSummary=Ncensor
      ProductLimitEstimates=PL
      Means=KMmeans
      Quartiles=quart
      Survivalplot=SurvivalPlotData
      ;

PROC LIFETEST DATA=ttv METHOD=PL ATRISK
  PLOTS=survival(ATRISK(ATRISKTICK)= 0 2 4 6 8 10);
  TIME aval*Cnsr(1);
  *---- stratified test ---*;
  STRATA ureter / GROUP=trt;
  ;
run;
where TRT is coded to HighDose vs LowDose
```

In additional, KM-survival analysis descriptive summary will also be provided for the overall. In this analysis, number of observations will not be the same as number of subjects.

Using data ‘SurvivalPlotData’ Kaplan-Meier survival curves will be presented for each treatment group along with number of subjects at risk at 0, 2, 4, 6, 8, and 10 minutes. The KM-survival plots will be prepared for each ureter and overall.

If data warrants, a Cox Proportional hazards (PH) model will be fitted to estimate hazards ratios (HR) between IC High dose vs IC Low dose using a stratified Cox PH model that includes main effect of treatment and stratified by ureter (left vs right). The HR estimate and 95% CI for the HR will be based on the Score Statistics. The p-value for treatment effect will be based on the Score Statistics because the p-value from the score statistics produced by PROC PHREG will be the same as the stratified log-rank test produced by PROC LIFETEST. In order to obtain HR 95% CI using the score statistics, an external SAS macro developed by based on Lin (2016)⁴ will be used (because the current SAS 9.4 does not have this computation option). Note the option of TIES=DISCRETE should be specified for SAS procedure PROC PHREG.

A summary table (**Table 14.2.4**) will include the following.

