- number (%) subjects with and without (censored) event from the left ureter and from the right ureter. This will allow each subject to be accounted once per treatment,
- Kaplan-Meier product limit estimates of quartiles of time to first event (25%, 50%, and 75% tiles and 95% CIs) and
- KM means (SE) of time to first event
- Hazard ratio (IC High/IC Low) and 95% Cis and p-value based on score test.

To compute the KM means and its standard error, in case a subject is censored at 10 minutes the option **TIMELIM** will be set to the maximum observed time in minutes when SAS procedure PROC LIFETEST is used to perform KM survival analysis. Hence, the calculated mean survival time will be the area under the Kaplan-Meier survival curve from 0 to this maximum observed time.

Below is an example of SAS syntax to estimate the difference between treatment groups IC High dose vs IC Lower dose using the external SAS macro HazardRatio. **This parameter will not applicable for Saline treatment.**

```
DATA CoxHS;
  set ttv;
  If CNSR=0 THEN EVENTYN=1;  *-- YES ---*;
  If CNSR=1 THEN EVENTYN=0;  *-- NO ---*;
  TIME=AVAL;
  if trt='IC High' then Treatment=1; else Treatment=0;
run;
```

⁴ Lin DY, Dai L, Cheng G, Sailer MO: On confidence intervals for the hazard ratio in randomized clinical trials. *Biometrics*, 75: 1098-1102, 2016. <http://dlin.web.unc.edu/software/HazardRatio/>

```
*---- use the macro to get Score HR 95% CI ****;
%HazardRatio (Data = CoxHS, Result=HR HL, Time = Time, Status =
EventYN, Ties=DISCRETE, Stratum = Ureter, Treatment = Treatment, Alpha
= 0.05, Accuracy = 0.00001);

data Result1;
    set HR_HL; if method='Score';
    HR=exp(estimate);
    HR_Lower=exp(Lower);
    HR_Upper=exp(Upper);
Run;
```

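### The TTV rule censors a ureter with an initial issue even when its visualization was seen and timed, which lengthens the reported time to visualization

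*SAP*

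**What the plan says.** SAP Section 2.1.1 lists time to visualization (TTV) of blue color after indigo carmine (IC) as a secondary efficacy endpoint. Section 3.8.3 sets the window: "TTV event is assessed only after IC treatment within 10 minutes after the injection start". It also sets the unit: "TTV will be derived for each subject following IC injection for each ureter separately".

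For a ureter where adequate visualization "did not occur for any reason, this subject will be censored for this analysis", Section 3.8.3 adds: "The censored time will be set to 10 minutes". No other TTV censoring time appears in the SAP.

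Section 3.8.3.1, on missing TTV data, closes with a separate rule. Where a subject initially had a problem with a ureter, "this subject will be censored for this analysis regardless if the issue(s) is or is not fixed during the procedure". This sentence states no censoring time and does not define an issue. Earlier in the same section, a ureter with a central score of 4 or higher is treated as having had the event and is not censored when its time is missing.

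Under Section 5.4, TTV "will be evaluated using the Kaplan-Meier Survival Analysis approach". Quartiles and a mean are reported, and for the mean "the calculated mean survival time will be the area under the Kaplan-Meier survival curve from 0 to this maximum observed time".

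**The concern.** Censoring is meant for a ureter whose event time is unknown beyond some point. Where an initial issue was resolved and blue jets were then timed inside the window, the event time is known and nothing is missing. The rule still turns that event into a non-event.

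Three consequences follow:

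- Under the 10-minute censoring time, Table 14.2.4 would show fewer ureters visualized and longer times than were observed. The stated purpose of the endpoint is to describe those times.
- The same ureter can score 4 or 5 with the central readers, and so support the primary endpoint, yet be reported as not visualized. If its event time is missing, two rules in Section 3.8.3.1 give opposite instructions: one says not censored, the other says censored.
- The rule speaks of the subject, while TTV is derived per ureter. The reader cannot tell whether an unaffected ureter on the other side also loses its observed time.

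**Working it through.** **No plan figure to reproduce.** The documents give no expected TTV, no TTV sample size and no rate of initial issues. The legible part of the sample-size section concerns conspicuity, and the rest is redacted.

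**Inputs from the SAP.** The window is 10 minutes (Section 3.8.3). About 95 subjects remain for efficacy (116 − 21, Section 3.2), with two ureters each, so 190 TTV observations.

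**Assumptions.** TTV is exponential with true median m = 5 minutes. A share f of ureters has an initial issue, with f from 2% to 15% (at 190 ureters, 5% is about 10 and 10% is 19). The issue is unrelated to TTV.

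**Reading A: censored at 10 minutes.** Before 10 minutes the Kaplan-Meier curve estimates S*(t) = f + (1 − f)S(t).

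- Median: setting S* = 0.5 gives m × ln[(1 − f)/(0.5 − f)] / ln 2. At f = 10%: 5 × ln(0.90/0.40)/ln 2 = 5 × 0.8109/0.6931 = 5.85.
- Mean to 10 minutes: with λ = ln 2/5 = 0.1386 and S(10) = 0.25, the true value is (1 − 0.25)/0.1386 = 5.41. The reported value is 10f + (1 − f) × 5.41.
- Proportion visualized by 10 minutes: (1 − f) × 75%.

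| Share f | Median (min) | Mean to 10 min | Visualized by 10 min |
|---|---|---|---|
| 0 | 5.00 | 5.41 | 75.0% |
| 2% | 5.15 | 5.50 | 73.5% |
| 5% | 5.39 | 5.64 | 71.3% |
| 10% | 5.85 | 5.87 | 67.5% |
| 15% | 6.40 | 6.10 | 63.8% |

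For exponential times the relative rise in the median (3%, 8%, 17%, 28%) is the same for any m, provided the shifted median stays within 10 minutes. Simulation with 190 ureters and 1,000 runs gave medians of 5.40 at 5% and 5.82 at 10%.

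**Less spread times.** With Weibull shape 2 and true median 5, the simulated median was 5.18 at 5% and 5.39 at 10%, a rise of about 4% and 8%. With Weibull shape 2.2 and scale 6 minutes, the 75th percentile is 6 × (ln 4)^(1/2.2) = 6.96. At f = 10% it falls where S = (0.25 − 0.10)/0.90 = 0.1667, giving 6 × (1.792)^(1/2.2) = 7.82.

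**Reading B: censored at the observed visualization time.** The ureter leaves the risk set at the moment it has its event, so the counted event hazard is (1 − f) times the true one. The exponential median becomes m/(1 − f): 5/0.95 = 5.26 and 5/0.90 = 5.56. Simulation gave 5.31 and 5.58. This is still too long.

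**Reading C: excluded, or censored at time 0.** Simulated medians were 5.06 and 5.02, and restricted means 5.42 and 5.41, so there is no bias beyond simulation error. The SAP does not say that this is intended.

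**Ordinary non-events.** When every non-event was watched for 10 minutes, censoring at 10 minutes and censoring at last observation gave identical results. If 10% of ureters were lost at a random time and still given 10 minutes, the median moved from 4.98 to 5.11 and the restricted mean from 5.39 to 5.51.

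**The case against.** The strongest defence is that a ureter with an initial problem does not show how the dye performs. Its time, measured from injection start, may include time spent on the repair, so declining to credit it is conservative. That is a fair reason to show results without such ureters. It does not justify keeping them in the risk set as ureters in which nothing was seen.

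Other points stand and limit the conclusion:

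- **Censoring time.** The 10 minutes is carried over from the non-event rule. An issue resolved only after the window leaves no event to discard.
- **Relation to TTV.** If affected ureters tend to visualize late, the quartiles move less, because a ureter already beyond a percentile does not shift it. The proportion visualized still falls by exactly the share of ureters whose in-window event is discarded.
- **The other ureter.** A reader might infer that it is certainly censored too. The SAP often writes subject for a ureter-level result, including in the event definition in Section 3.8.3.1, so the wording is ambiguous and no more.
- **Ordinary non-events.** A reader might infer that giving them 10 minutes is itself a bias. It is correct when the ureter was watched throughout. The window is 10 minutes, and the efficacy set requires that "a video approximately 10 minutes in length is available after each treatment".
- **Net direction.** A reader might infer that TTV as a whole is biased long. Other rules in Section 3.8.3.1 pull both ways: an event with no time is placed at 10 minutes, while a missing start time is set to injection completion, which shortens TTV. The net is not settled.

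The protocol amendment and the case report form might define an issue. Neither is among the documents available.

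**Conclusion.** The concern holds for the initial-issue rule alone. As written, the rule discards a visualization timed within the window. Under the SAP's only censoring time it reports that ureter as event-free to 10 minutes, and censoring at the observed time would also lengthen TTV. Only exclusion or censoring at time 0 would avoid the bias.

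The size depends on a share that the documents do not give. On the exponential assumption the median rises by about 3% at 2% affected and 17% at 10%. With less spread times the rise is roughly half as large. Both figures assume that the issue is unrelated to TTV.

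The change should be made, but it is not critical. TTV is a descriptive secondary endpoint outside the type I error control of Section 3.4, the rule applies alike to both doses, and the primary conclusion is untouched.

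**What to change.** Amend SAP Section 3.8.3.1 as follows:

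1. In the main TTV analysis, count a visualization recorded within 10 minutes of injection start as an event at its observed time, whatever the initial issue.
2. State that the rule concerns only the affected ureter, define what counts as an initial issue, and state the censoring time for an affected ureter with no visualization in the window.
3. Add a sensitivity analysis of Table 14.2.4 that excludes ureters with an initial issue, and report their number by dose.

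On the assumptions above with 10% affected, step 1 returns the median from about 5.85 to 5.0 minutes and the 10-minute mean from 5.87 to 5.41. The cost is SAP wording, one derivation and one extra table. The visualization times are already captured, though the initial-issue flag needs to be available per ureter. The small downside is that an observed time in a repaired ureter may include repair time, which step 3 addresses. The 10-minute censoring of ordinary non-events can stay.
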